5.6 Design and plan of the study

Phase I clinical trial, controlled, of parallel groups, double blind with randomization, exploratory.

5.6.1 Discussion of the study design

The design of the study (clinical trial) is considered the highest quality standard in the data when it is sought to explore the effect of an intervention. The phase of pharmacological development (phase I) corresponds to the objective of the study which is to assess safety and tolerability, so that the intervention time is short and the sample size required is less than that of a clinical efficacy trial. The presence of parallel groups allows the comparison between the intervention groups on the outcome variables. Blinding and randomisation allow to reduce biases that are incurred with other designs, eg. selection bias, evaluation bias, among others.

6. Material and methods. Participants, interventions and variables

6.1 Study Center

The present study will be performed in ophthalmology offices duly equipped and registered for their proper functioning. According to the needs of the sponsor, these may be private or public, be attached to a hospital or clinic or be independent.

6.1.1 Organization of the center

Each study center will have a principal investigator (PI). The PI is the ophthalmology specialist in the clinical study.

The PI is responsible for forming a multidisciplinary research team to carry out the clinical study according to protocol, under its scientific guidance. It is the prerogative of the IP the design of the organization of its center and the selection of the personnel that will perform the functions. Notwithstanding, the minimum organization of the research team requested by the sponsor requires the figure of sub-researcher, study coordinator and pharmacist. (See Figure 1 Minimum organization of the center)

Any person to whom the PI designates, under his / her responsibility, a part of the follow-up of the study (co-investigator, under-researcher, nurse, etc.) or a specific function of participation in the study (pharmacist, administrative assistant, study coordinator, etc.) should appear in the format of "Delegation of Responsibilities".

[figure not shown]
CONFIDENTIAL

Figure 1 Minimum organization of the center

The "Delegation of Responsibilities" and the "Organizational Chart of the Center" must be delivered to the sponsor before the start of the study and updated if the members or their responsibilities are changed.

6.1.2 Documentation to be delivered to the sponsor

The PI must deliver to the sponsor, before the start of the study:

- Curriculum vitae updated, in Spanish, dated and signed (maximum 10 pages), of the IP and the staff that integrates its organizational chart of the center.
- Copy of IP academic certifications (degree certificate and specialty diploma in ophthalmology, federal professional certificates)
- Copy of academic certifications of the maximum degree obtained, from each one of the members of your research team, that cover their capacity to perform the delegated functions.
- Copy of operating notice or similar issued by corresponding regulatory entity (When applicable)
- Certificate of good clinical practice in force. If the issuing institution does not specify the validity period in the certificate, the date of issue of the certificate must not exceed one year

6.1.3 Closure of the center

The closing of the center will be carried out once the last visit of the last included subject previously agreed between the sponsor and the IP has been made. The closing process will be according to the internal operating procedures of the sponsor.

It is the sponsor's prerogative to prematurely close a study center, it must inform the IP the reasons for the closure.

6.2 Eligibility criteria

6.2.1 Inclusion criteria

- Signed informed consent.
- Systemically and ophthalmologically healthy subjects evaluated during the clinical history.
- Age between 18 to 45 years.
- Both genders.
- Blood tests [complete blood count (BHC), three element blood chemistry (QS) and liver function tests (PFH)] within normal parameters specified by the reference laboratory with a lower and upper margin of 10%.

- Vital signs within normal parameters. (Vital signs at rest: blood pressure \leq 139/89 mmHg, heart rate 60 -100 beats per minute and respiratory rate of 12-24 breaths per minute).
- - Visual capacity 20/30 or better, in both eyes.
- - Intraocular pressure \geq 11 and \leq 21 mmHg.

6.2.2 Exclusion criteria

6.2.2.1 General criteria

- Subjects with a history of hypersensitivity to any of the components of the research products.
- Subject users of topical ophthalmic medications of any pharmacological group.
- Subject users of medication by any other route of administration.
- Pregnant or lactating women.
- Women of childbearing age, who do not ensure a hormonal contraceptive method or intrauterine device during the study period or without a history of bilateral tubal obstruction, oophorectomy or hysterectomy; as fertile age we understand women who have not had their menopause, defined as 12 months since the last menstruation in women over 40 years.
- Subjects with participation in clinical research studies 90 days prior to inclusion in the present study.
- Diagnosis of liver disease or elevation to three times the normal upper value of any of the following liver enzymes: aspartate transferase (AST), alanine transferase (ALT) or bilirubin.
- Inability to attend or answer the evaluations made in each of the visits.
- Positive smoking (specified as cigarette consumption regardless of amount and frequency)
- Positive alcoholism (specified as the consumption of alcoholic beverages, regardless of quantity and frequency, during the study intervention period).
- Contact lens users.
- Occlusible iridocorneal angle, defined as a trabecular mesh visible in less than 90 ° of the angular circumference to gonioscopy.

6.2.3 Elimination criteria

- Withdrawal of the consent letter under information.
- Presentation of a serious adverse event.
- No tolerability or hypersensitivity to any of the compounds used during the tests (fluorescein, green lysine, tetracaine)
- No tolerability or hypersensitivity to any of the investigational drugs.
- Adherence <50% determined by the diary of the subject, of the established dose of the pharmacological intervention in any of the visits.

6.2.4 Identification of the subject

The patients of the study will be identified by a number and the initials of their name.

The initials of the study subject will be obtained starting with the first letter of the name, followed by the first letter of the first surname and the first letter of the second surname, obtaining maximum

three letters, in case the person has two names or a compound surname the first letter will always be used.

[figure not shown]
Example:

1. Arieh Daniel Mercado Carrizalez
 - a. Iniciales: AMC
2. Juan De la Torre Orozco
 - a. Initials: JDO

In the counting stage, the participant number will be assigned consecutively, using 3 consecutive digits. Once the subject has been selected, he will be assigned a number with which he will be identified throughout the study. Said code will be composed of eight numbers in the following order from left to right:

- three digits of the molecule under study according to the denomination by the sponsor.
- two digits corresponding to the research center number.
- three digits of the number consecutive to its inclusion assigned in the research center.

Example:

6.3 Intervention

6.3.1 Managed treatments

6.3.1.1 Treatment under study

The characterization and stability tests of the treatment under study are issued by Sophia Laboratories, S.A. of C.V and will be found in the certificates contained within the master folder of the study.

More detailed information can be found in the researcher's manual.

- PRO-174

- Active substance: Levofloxacin 0.5%
- Pharmaceutical form: ophthalmic solution
- Prepared by: Sophia Laboratories, S.A. of C.V
- Dosage: 1 drop in both eyes, 8 times a day during the waking period
- Description of the solution: transparent solution, free of visible particles.
- Description of container: sterile multi-dose bottle

Table 4. Quali-quantitative formulation of PRO-174

Type of agent	Amount mg/mL	Function
Levofloxacin hemihydrate ⁽¹⁾	5.0	Active principle
Sodium Citrate Dihydrate	Without showing	Additive
Citric acid monohydrate	Without showing	Additive
Disodium Edetate Dihydrate	Without showing	Additive
Sodium chloride	Without showing	Additive
Benzalkonium Chloride ⁽²⁾	0.1	Additive
Fumante Hydrochloric Acid ⁽³⁾	Without showing	Additive
Sodium Hydroxide ⁽⁴⁾	Without showing	Additive
Water for preparation of injectables c.b.p. ⁽⁵⁾	1.0 ml	Vehicle

Quali-quantitative formulation of the product under investigation PRO-174. The concentration of the active ingredients is shown, as well as the substances that act as an additive.

OBSERVATIONS:

(1) Equivalent to Levofloxacin (adjustment made by power).

(2) 50% solution.

(3) 4N hydrochloric acid solution.

(4) 4N sodium hydroxide solution.

(5) c.b.p. (how much is enough for).

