Creation date: August 2016

Phase I clinical study, to evaluate the safety and tolerability of the ophthalmic solution PRO-174 versus Sophixín Ofteno[®], elaborated by Sophia Laboratories, S.A. of C.V. on the ocular surface of ophthalmologically and clinically healthy subjects

Protocol code: SOPH174-0816/I

Protocol version: 1.1

Date of the version: 18/04/2017

Registry: 173301410A0149/2017

Sponsor: Laboratorios Sophia, S.A. de C.V.

1. Summary

Title of the study:	
Phase I clinical study, to evaluate the safety and tolerability of the ophthalmic solution PRO-174 versus Sophixín Ofteno®, elaborated by Sophia Laboratories, S.A. of C.V. on the ocular surface of ophthalmologically and clinically healthy subjects.	
Protocol code:	Creation date:
SOPH174-0816/I	22/08/2016
Protocol version:	Date of the version:
1.1	18/04/2017
Therapeutic indication:	
Eye antibiotic	
Study period:	Development phase: I
3 to 4 months	
Goals:	
To evaluate the safety and tolerability of the formulation PRO-174 manufactured by Sophia Laboratories, S.A. of C.V. on the ocular surface of clinically healthy subjects.	
Hypothesis:	
The ophthalmic solution PRO-174 presents a safety and tolerability profile similar to the comparator in healthy subjects.	
Methodology:	
Phase I clinical trial, controlled, of parallel groups, double blind, randomized, exploratory.	
Number of patients:	
30 subjects, divided into 2 groups [15 subjects (30 eyes) exposed per group]	
Diagnosis and main inclusion criteria:	

 - Signed informed consent. - Systemically and ophthalmologically healthy subjects - Age between 18 to 45 years. -Both genders. - Blood tests [complete blood count (BHc), three element blood chemistry (QS) and liver function tests (PFH)] within normal parameters specified by the reference laboratory with a lower and upper margin of 10%. - Visual capacity 20/30 or better, in both eyes.- -Intraocular pressure ≥ 11 and ≤ 21 mmHg. 	

Test product, dose and route of administration, lot number:
 
 - PRO-174. Levofloxacin 0.5% ophthalmic solution. Prepared by Sophia Laboratories, S.A. of C.V, Zapopan, Jalisco, Mexico. - Dosage: 1 drop every 2 hours during the waking period (8 daily applications), on day 1 and 2; continuing with 1 drop every 4 hours during the waking period (4 daily applications) from day 3 to 7. Both eyes. - Route of administration: ophthalmic

Duration of treatment: 7 days

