6.3.2.1 Procedure to monitor adherence

Adherence monitoring will be done in the research center through the diary of the subject, will be done as follows:

$$Ad = (A_r)100/A_i$$

Ad = Adherencie

A_r = Registered applications

A_i = Applications indicated for the intervention

This result will allow the PI to determine if the subject continues in the study according to the stipulations of the elimination criteria.

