6.3.2.2 Procedure to determine adherence

The final adhesion will be determined by the sponsor by means of the weight of the bottle.

Before delivering the medication to the research center, the weighing of the bottles to be delivered must be carried out. After the return of the medication by the center will be weighing. The weighing will be carried out according to the procedures regulated by the sponsor.

The adhesion will be calculated considering: the weight of the empty bottle, the weight of the drop, the weight of the bottle with the content, the calculation of the total of drops to be applied during the entire time of intervention and the total weight of the drops applied. The following simplified formula will be used:

$$Ad = \frac{(P_i - P_f)100}{P_T}$$

Where:

Ad = adhesion

P_i = weight of the bottle delivered to the subject at the start

P_f = weight of the bottle returned by the subject

P_T = weight of the posology indicated for the intervention.

$$P_T = (P_g)G$$

Where:

P_g = weight of the drop of the intervention, determined by the department of research and development

G = number of drops indicated for the intervention.

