6.3.4.1 Delivery and reception

The delivery will be made in closed cardboard boxes by means of a courier service or directly by the sponsor's staff to the address of the research center according to the study plan.

The reception will be exclusively carried out by the research center team, including the researcher. You must check the good condition of the primary packaging (box). In the event that it shows alterations or defects in its integrity that from its judgment could have damaged the content, it should report it to the sponsor. If the package does not show significant defects, it will proceed to open it.

Inside you must locate the acknowledgment document and the logger (data logger) of temperature and humidity. You should check that the registered temperature and humidity comply with the specifications for transport and shelter (see section 6.3.4.2 Storage). Verify the content (interventions) with what is reported in the document. In case the document corresponds to the content, it will sign the receipt and send it to the sponsor. Otherwise, notify the sponsor.

In the study center, the personnel assigned by the IP will deliver to the inpatients the corresponding treatment, sufficient to complete the indicated applications. The center must register the medicine delivered.

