6.3.5 Overdose

Overdosage with PRO-174 or Sophixin Ofteno® is not likely to cause effects that threaten function, the organ or less, life. The above, because increasing the number of drops instilled in an application will not increase the exposure to the drug, since the lacrimal lake does not have the capacity to contain a volume greater than one drop, spilling the rest. In case of increasing the frequency of instillations, an increase in the incidence of adverse reactions could be seen (eg, foreign body sensation, headache, photophobia, etc).

For purposes of this protocol we understand as overdosage the increase in 25% of the indicated instillations. That is, 10 or more applications per day on days 1 and 2, or 5 or more applications on days 3 to 7.

1. The report of the overdose will be made in the following tenor:
2. How a deviation to the protocol. The regime instructed in the protocol was not followed.
3. How an EA. Only if it is associated with signs and symptoms.
4. How an EAS. If you meet the criteria to be classified as an EAS.

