6.5.1 Procedures to be performed per visit

6.5.1.1 Scrutiny visit

- **Signature of informed consent:** refers to the signing of the written informed consent document. See 10.3 Consent.

- General and ophthalmological clinical history: refers to the technical, clinical and legal document in which the patient's health conditions, medical acts and other procedures performed on the patient are recorded chronologically. It includes the anamnesis and comprehensive ophthalmological exploration that allows to discern the patient's eligibility. If the patient is taken from the established consultation of the study center, he / she will be able to use the existing clinical history, only having to perform an update.
- Taking laboratory samples: see 6.4.3.11 Laboratory tests.
- Pregnancy test: see 6.4.3.11 6.4.3.10 Pregnancy test.
- Eligibility criteria: refers to the review by the IP, where it states that the subject can be included in the study by meeting the inclusion criteria and not meeting the exclusion criteria. See 6.2 Eligibility criteria
- Intraocular pressure: see 6.4.3.5 Intraocular pressure
- Visual ability: see 6.4.3.1 Visual capacity
- TRL: see 6.4.3.9 Rupture time of the tear film
- Integrity of ocular surface: see 6.4.3.3 Integrity of ocular surface:
- Eye symptoms: 6.4.3.8 Ocular symptomatology
- Subsequent segment: see 6.4.3.6 Subsequent segment
- Vital signs: see 6.4.3.7 Vital signs
- Adverse events: see 6.4.3.4 Presence of adverse events6.5.1.2 Visita basal
- Review of laboratory tests: refers to the review and analysis by the IP of the results of the BH, QS and PFH. See 6.4.3.11 Laboratory tests.
- Eligibility criteria: with the laboratory results, the subject's profile will be finalized for inclusion or not.
- Assignment: It refers to determining the intervention that the patient will follow during the study. It will be done according to section 7. Methods. Assignment of the intervention. This assignment will be made at the baseline visit (day 0) and will go along with the indication to start the treatment period the next day (day 1).
- Delivery of intervention: Refers to the delivery of the product under investigation to the patient of the study, by the research center. It will be done according to sections 6.3.1 Managed treatments and 6.3.4.1 Delivery and reception.

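### The treatment sections (6.3.1.1 and 6.3.1.2) omit the step-down from 8 to 4 applications a day; followed for 7 days they double the dose on days 3-7 and meet the protocol's own overdose definition

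*Combined protocol and SAP*

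**What the plan says.** The combined protocol and SAP describes the dose in three places.

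- **Section 1, Summary.** For each product: "1 drop every 2 hours during the waking period (8 daily applications), on day 1 and 2; continuing with 1 drop every 4 hours", the second stage being 4 applications a day on days 3 to 7, in both eyes. Treatment lasts 7 days.
- **Sections 6.3.1.1 and 6.3.1.2.** For each product: "Dosage: 1 drop in both eyes, 8 times a day during the waking period". No days are attached and no reduction is mentioned.
- **Section 6.3.5, Overdose.** Overdose is 25% above the indicated instillations, spelled out as follows: "That is, 10 or more applications per day on days 1 and 2, or 5 or more applications on days 3 to 7". It is to be reported as a protocol deviation, and as an adverse event if signs or symptoms accompany it.

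The visit procedures in section 6.5.1 say of handing over the product: "It will be done according to sections 6.3.1 Managed treatments and 6.3.4.1 Delivery and reception". Section 6.3.4.1 adds only that staff "will deliver to the inpatients the corresponding treatment, sufficient to complete the indicated applications".

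The adherence formulas in 6.3.2.1 and 6.3.2.2 divide by the indicated amount without giving a number: "A_i = Applications indicated for the intervention" and "G = number of drops indicated for the intervention". Adherence then decides elimination (section 6.2.3: "Adherence <50% determined by the diary of the subject, of the established dose of the pharmacological intervention in any of the visits") and entry to the analysis (section 8.3.1: above 60%).

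**The concern.** The chosen dose is not in dispute. The protocol states two different regimens, and the incomplete one stands in the section that defines the treatments. In the text available, the full by-day schedule is written out only in the summary.

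Staff who follow 6.3.1 would instruct subjects to keep using 8 applications a day after day 2. By the protocol's own rule, that is an overdose and a deviation on each of days 3 to 7. Section 10.5 lists an error in dosing study medication as an example of a major deviation.

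Exposure also bears on the endpoints. Section 6.3.5 accepts that more frequent instillation could raise the incidence of adverse reactions, and it names foreign body sensation. Adverse events and foreign body sensation are both primary outcomes (6.4.1.1 and 6.4.1.2). With 15 subjects per arm, mixed readings of the dose would add variation in exposure within each arm.

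**Working it through.** **Inputs.** Summary: 8 a day for 2 days, then 4 a day for 5 days, 7 days in all. Sections 6.3.1.1 and 6.3.1.2: 8 a day, no duration given. Section 6.3.5: overdose at 25% above the indicated number, with limits of 10 and 5 a day. Cuts: below 50% (6.2.3) and above 60% (8.3.1).

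**Step 1: reproduce the plan's overdose limits.** Limit = 1.25 × indicated daily applications.

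- Days 1-2: 1.25 × 8 = 10, as stated.
- Days 3-7: 1.25 × 4 = 5, as stated.
- Under a flat 8 a day the limit would be 10 on every day, and a limit of 5 would have no basis.

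So 6.3.5 was written for 8-then-4, and 6.3.1 is the text in error.

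**Step 2: applications per eye under each reading.** The flat course takes its 7 days from the summary. No section states a total of 56, so that figure is an assumption.

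| | 8 then 4 | Flat 8 | Ratio |
|---|---|---|---|
| Days 1-2 | 2 × 8 = 16 | 2 × 8 = 16 | 1.0 |
| Days 3-7 | 5 × 4 = 20 | 5 × 8 = 40 | 2.0 |
| Whole course | 36 | 56 | 56/36 = 1.56 |
| Drops, both eyes | 72 | 112 | 1.56 |

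**Step 3: compare with the overdose limit.** On days 3-7, 8 a day is above the limit of 5, so all five days count as overdose. On days 1-2, 8 is below 10.

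**Step 4: secondary effect on adherence.** This arises only if a subject dosed 8-then-4 is scored against the flat total of 56, and it uses application counts.

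- Full adherence: 36/56 = 64.3%, which passes both cuts.
- Above 60%: against 36, at least 22 are needed (22/36 = 61.1%; 21/36 = 58.3%). Against 56, at least 34 are needed (34/56 = 60.7%; 33/56 = 58.9%). Subjects with 22-33 applications would be left out.
- Below 50%: against 36, this means 17 or fewer (17/36 = 47.2%). Against 56, it means 27 or fewer (27/56 = 48.2%). Subjects with 18-27 applications would be eliminated.

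Visit 1 may fall on days 2 to 4. Cumulative denominators counted through the visit day are:

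- Day 2: 16 under both readings.
- Day 3: 20 against 24. Only 10 or 11 of 20 changes class (10/24 = 41.7%, 11/24 = 45.8%).
- Day 4: 24 against 32. Subjects with 12-15 of 24 change class (16/32 = 50%).

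**The case against.** The strongest reply is that the intended regimen can be recovered. Section 6.3.5 lies within the same section 6.3 and separates days 1-2 from days 3-7. The background (Table 3, footnote b) shows the same pattern of every 2 hours then every 4 hours in cited levofloxacin trials, though only to day 5. Sections 6.3.1.1 and 6.3.1.2 read largely as product descriptions, and the cross-reference from the visit procedures concerns handing over product. The diary, the researcher's manual, the printed calendar given to subjects and the study diagram (Figure 2) could not be seen, and any of them may carry the step-down.

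These points lower the chance that subjects would be misdosed, but they do not remove the conflict. The two sections contain an explicit dosage line that is wrong from day 3 on, and a reader should not have to infer the dose from an overdose limit.

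The objection is stronger on adherence. The scenario requires dosing by one section and scoring by another. Final adherence is computed by the sponsor from bottle weight, and section 8.3.1 does not say whether the 60% cut uses weight or diary. A sponsor that wrote limits of 10 and 5 is unlikely to set G from a flat regimen. That part is a side effect and does not carry the conclusion.

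Section 6.3.5 also says overdose is unlikely to threaten function, organ or life, and this is accepted.

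**Conclusion.** The concern holds and must be fixed. Sections 6.3.1.1 and 6.3.1.2 contradict the summary and section 6.3.5 on the dose for five of seven days. Followed for the 7-day course, they give 40 instead of 20 applications per eye on days 3-7 and 56 instead of 36 overall, with every one of those five days meeting the protocol's overdose definition.

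The contradiction and the doubling follow directly from the text. The course total of 56 rests on applying the summary's 7 days to a section that states no duration. Whether any subject would actually be misdosed cannot be judged without the diary and the manual. No bias between arms is claimed, because the wording is the same for both products.

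**What to change.** - In 6.3.1.1 and 6.3.1.2, write the regimen by day to match the summary: in both eyes, 1 drop every 2 hours while awake (8 applications a day) on days 1-2, then 1 drop every 4 hours while awake (4 applications a day) on days 3-7.
- In 6.3.2.1, state A_i = 36 applications per eye for the whole course. For Visit 1, give the cumulative number due for its whole window (8, 16, 20 and 24 through days 1, 2, 3 and 4) and say whether the visit day itself is counted.
- In 6.3.2.2, state G = 72 drops for both eyes.
- Check that the subject's diary, the researcher's manual, the printed calendar and the study diagram agree with this.

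The cost is wording in four sections and a check of these documents. No subjects, visits or procedures are added.
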